6.6.2. Laboratory Data

Incidence of laboratory test (including hematological, clinical chemistry, urinalysis tests) abnormalities (without regard to baseline abnormality, with normal baseline and abnormal baseline respectively) will be reported.

Baseline value and CFB for the laboratory tests of interest listed in Section 3.5.2.1 will be summarized descriptively via the method stated in Section 5.2.2.

6.6.3. Vital Signs Data

Baseline values, absolute values and changes from time-matched baseline values in supine systolic, supine diastolic blood pressure and pulse rate will be summarized by treatment, time post-dose and day with descriptive statistics stated in Section 5.2.2 (according to CaPS). Tables will be paged by parameter. Baseline is as defined in Section 3.5.3.

Maximum absolute values and maximum changes from time-matched baseline for vital signs will also be summarized descriptively as stated in Section 5.2.3 using categories as defined in Appendix 1 (Section 9.1).

All planned and unplanned post dose time points will be counted in these categorical summaries. The time-matched double differences in vital signs obtained following the Day 1 treatment, as defined in [Section 3.5.3](#), will be summarized (N, mean, 90% confidence interval) for each treatment and time point.

Mean time-matched double differences in vital signs will be plotted against time post-dose for Day 1 and Day 56 separately. On each plot there will be 1 line for each treatment.

6.6.4. ECG Data

Baseline values, absolute values and changes from time-matched baseline in QT, heart rate, QTcF interval, PR interval and QRS complex will be summarized by treatment and time post-dose and day with descriptive statistics stated in [Section 5.2.2](#) following CaPS. Tables will be paged by parameter. Baseline is as defined in [Section 3.5.4](#).

Maximum increase from time-matched baseline for QTcF and heart rate will be summarized by treatment, according to sponsor reporting standards.

The number (%) of participants with maximum absolute value and maximum increase from baseline for QTcF, PR and QRS (see Appendix 1 in [Section 9.1](#)) will be summarized using method stated in [Section 5.2.3](#).

All planned and unplanned post-dose time-points will be counted in these categorical summaries.

The time-matched double differences in QT interval, heart rate, QTcF interval, PR interval, and QRS complex measures obtained following the Day 1 treatment, as defined in [Section 3.5.4](#), will be summarized (N, mean, 90% confidence interval) for each treatment and time point.

6.6.5. Mean time-matched double differences in ECG parameters will be plotted against time postdose for Day 1 and Day 56 separately. On each plot there will be 1 line for each treatment. Physical Examination

Physical examinations will be summarized by treatment and dose level in accordance to CaPS.

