While there were isolated values for laboratory tests, vital signs and ECG intervals outside of the reference ranges, no clear adverse trends were apparent in these parameters. As has been reported for marketed GLP-1R agonists, increases in heart rate have been observed, with mean increases ranging from 5 to 15 bpm across doses administered to date, and most heart rate values were within the normal range. In summary, PF-06882961 was generally safe and well tolerated in C3421002, with a safety profile in line with marketed GLP-1R agonists.

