### 9.2. Sample Size Determination

The sample size of this study is not based on statistical considerations. A sufficient number of participants will be screened to achieve approximately 20 participants randomly assigned to study intervention and at least 8 evaluable participants completing multiple titration dosing up to 120 mg in order to evaluate the primary endpoints of  $AUC_{24}$  and  $C_{max,ss}$  at Day 56.

The participants will be randomized at a 3:1 ratio with 15 participants being randomized to PF-06882961 and 5 participants being randomized to placebo for the purpose of descriptively evaluating the safety CCI [REDACTED] endpoints. CCI [REDACTED]

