3.5.3. Vital Signs

Vital sign measurements (blood pressure and pulse rate) will be taken as detailed in the schedule of activities given in the protocol. The average of the triplicate measurements at each appropriate assessment time will be calculated for each blood pressure and pulse rate, if applicable.

Changes from time-matched baseline for supine systolic and diastolic blood pressure and pulse rate will be calculated for each post baseline measurement. Baseline is defined as the time-matched value from the average of the triplicate recordings on Day -1.

In addition, the time-matched double difference in supine blood pressures and pulse rate measurements is calculated in the following steps: (1) subtract predose value on Day 1 from all postdose values; (2) subtract the value at 0 hours on Day -1 from all other values on Day 1; (3) take the difference between the adjusted postdose value in (1) and its time-matched value in (2).

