3.5.4. Electrocardiograms

Standard 12-lead ECG (including heart rate, PR, QT, QTcF intervals and QRS complex) will be obtained at times detailed in the schedule of activities given in the protocol. The average of the triplicate readings collected at each appropriate assessment time will be calculated for each ECG parameter, if applicable.

Change from time-matched baseline for heart rate, PR, QT, QTcF intervals and QRS complex will be calculated for each post baseline measurement. Baseline is defined as the time-matched value from the average of the triplicate recordings on Day -1.

In addition, the time-matched double difference in heart rate, PR, QT, QTcF and QRS measures is calculated in the following steps: (1) subtract predose value on Day 1 from all postdose values; (2) subtract the value at 0 hours on Day -1 from all other values on Day -1; (3) take the difference between the adjusted postdose value in (1) and its time-matched value in (2).

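### No active-minus-placebo estimate is specified for ECG or vital signs: the 90% intervals are within-arm and cover only the single 10 mg dose on Day 1

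*SAP*

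**What the plan says.** **Definition.** SAP 3.5.4 builds the ECG double difference in three steps: "1) subtract predose value on Day 1 from all postdose values"; then "2) subtract the value at 0 hours on Day -1 from all other values on Day -1"; then "take the difference between the adjusted postdose value in (1) and its time-matched value in (2"). SAP 3.5.3 gives the same recipe for blood pressure and pulse rate, except that its second step reads "2) subtract the value at 0 hours on Day -1 from all other values on Day 1".

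**Reporting of double differences.** Under SAP 6.6.3 and 6.6.4, those following the Day 1 treatment "will be summarized (N, mean, 90% confidence interval) for each treatment and time point". Means are also plotted for Day 1 and Day 56, with one line per treatment. No interval is stated for Day 56.

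**Reporting of change from time-matched baseline.** This is tabulated by treatment, time and day with the statistics of SAP 5.2.2: n, mean, SD, median, minimum and maximum. No interval is included.

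**Purpose of placebo, and the known signal.** Protocol 9.2 says the 15 v 5 split is "for the purpose of descriptively evaluating the safety" endpoints. Protocol 2.2.2.1 reports heart-rate rises, with "mean increases ranging from 5 to 15 bpm across doses administered to date". Protocol 9.1 states that no hypothesis tests are planned.

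**The concern.** The word double suggests a placebo-corrected quantity, as in some ECG analyses. Here it means two subtractions within the same participant. Placebo participants get their own rows and their own line on the plot, but the visible text never subtracts one arm from the other.

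This matters most at the higher doses. By Day 56 a participant has been through several inpatient stays and eight weeks of study life. A within-arm change from Day -1 then combines the drug effect with anything else that has shifted over that time. The randomised comparison removes whatever shift the arms share, and the 5 placebo participants are there to support it. Without a stated estimate and interval, readers must judge by eye whether a heart-rate rise exceeds that in placebo, and how uncertain the gap is.

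**Working it through.** **Inputs.** 15 active and 5 placebo participants, and at least 8 active evaluable at 120 mg (Protocol 9.2). Day 1 is a single 10 mg dose (SAP 3.1). ECG and vital signs are taken at 0, 1, 2, 4, 8 and 12 h on Days -1, 1, 21, 35 and 56 (Protocol Table 2). The sample size is declared non-statistical and no SD is given, so there is no precision figure in the plan to reproduce. I assume an SD of change of 6 to 10 bpm, equal in both arms.

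**1. What each double difference removes.** Write Y(d,t) for a participant's value on day d at time t.

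- ECG, Day 1: [Y(1,t) − Y(1,0)] − [Y(−1,t) − Y(−1,0)]. There is no placebo term. With no drug effect, a constant 5 bpm shift between Day -1 and Day 1 returns 0. A 5 bpm change that builds up within Day 1 returns 5.
- ECG, Day 56, as written: [Y(56,t) − Y(1,0)] − [Y(−1,t) − Y(−1,0)]. A 5 bpm drift over the eight weeks returns 5, so it stays in full.
- Change from time-matched baseline, any day d: Y(d,t) − Y(−1,t). Any drift since Day -1 stays in full. Subtracting the placebo mean removes the part common to both arms.
- Vital signs, Day 1, as printed: [Y(1,t) − Y(1,0)] − [Y(1,t) − Y(−1,0)] = Y(−1,0) − Y(1,0). The post-dose value cancels, so a true 10 bpm pulse-rate effect returns 0.

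**2. Precision of the missing contrast (90% CI half-widths, in SD units).**

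- Active alone, n = 15: t(0.95,14)/√15 = 1.761/3.873 = 0.455.
- Placebo alone, n = 5: t(0.95,4)/√5 = 2.132/2.236 = 0.953.
- Active minus placebo, 15 v 5: t(0.95,18) × √(1/15 + 1/5) = 1.734 × 0.516 = 0.895.
- Active minus placebo, 8 v 5: t(0.95,11) × √(1/8 + 1/5) = 1.796 × 0.570 = 1.024.

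In bpm:

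| Assumed SD | Active minus placebo, 15 v 5 | Active minus placebo, 8 v 5 | Placebo alone (n = 5) |
|---|---|---|---|
| 6 | 5.4 | 6.1 | 5.7 |
| 8 | 7.2 | 8.2 | 7.6 |
| 10 | 9.0 | 10.2 | 9.5 |

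**3. Chance that the 90% CI lies wholly above zero** (noncentral t, range over SD 10 down to 6):

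| True difference | 15 v 5 | 8 v 5 |
|---|---|---|
| 5 bpm | 0.24 to 0.46 | 0.21 to 0.39 |
| 10 bpm | 0.59 to 0.93 | 0.50 to 0.86 |

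**4. Number of intervals.** Six times × four days × four parameters (heart or pulse rate, systolic BP, diastolic BP, QTcF) = 96. With no effect anywhere, about 0.10 × 96 = 9.6 would exclude zero by chance.

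**The case against.** **The study is descriptive.** No tests are planned, and parallel arm summaries arguably meet the stated purpose. That stands as a reason not to add tests. It does not rule out a descriptive difference with an interval, since the SAP already plans 90% intervals within each arm.

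**The contrast can be derived.** Placebo n, mean and SD are tabulated next to active, and anyone can compute the difference and its interval from them. This is correct: no data are lost. A reader might infer that a heart-rate effect cannot be separated from drift at all. The documents do not support that, because placebo is tabulated and plotted alongside.

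**Drift does not enter the intervals that are planned.** A reader might also infer that the quoted 90% intervals are contaminated by eight weeks of drift. They are not. They cover Day 1 only, within the same inpatient stay as Day -1, and the ECG formula removes a constant shift between those two days. The drift argument applies to Days 21, 35 and 56, where no interval is planned.

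**Five placebo participants give little precision.** This stands in part. The contrast is about twice as wide as the active-arm interval (0.895 v 0.455 SD), though at 15 v 5 it is slightly narrower than the placebo-alone interval already planned for Day 1 (0.953 SD). The 5 to 15 bpm range spans all doses given to date and is not specific to 10 mg.

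**Some SAP text is redacted.** Part of SAP 5.2.2 is blacked out and the sponsor's standard outputs are not shown, so the point is limited to the visible text. The double-difference definitions and their summaries are fully visible.

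**Conclusion.** The point holds as a gap in estimation. In the visible SAP, no active-minus-placebo difference is specified for ECG or vital signs. The 90% intervals are within-arm and stop at the single 10 mg dose. At the target dose, 120 mg BID on Day 56, there are per-arm summaries and mean plots with no interval, and those changes keep any drift since Day -1.

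The missing contrast would be moderately informative. Its half-width is 0.895 SD at 15 v 5 and 1.024 SD at 8 v 5. It would often separate a 10 bpm effect from zero but would not do so reliably for 5 bpm. The bpm figures rest on an assumed SD of 6 to 10 bpm, equal in both arms. Removal of drift rests on the drift being common to both arms, which randomisation supports on average but 5 participants cannot guarantee.

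The vital-sign definition is a separate and definite inconsistency. As printed, its Day 1 double difference carries no post-dose information.

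**What to change.** 1. In SAP 6.6.3 and 6.6.4, add the active-minus-placebo difference in mean change from time-matched baseline, with a 90% CI, for heart rate or pulse rate, systolic and diastolic BP, and QTcF. Report it at the nominal times on Days 1, 21, 35 and 56, which share the Day -1 sampling grid. Label it descriptive and unadjusted for multiplicity, and identify Day 56 as the target-dose result.
2. Reconcile step 2 of the double difference in SAP 3.5.3 with that in SAP 3.5.4, so that both name the day intended.

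The cost is SAP wording and a few extra tables, with no new data. The downside is wide intervals, resting on 5 placebo participants, some of which will exclude zero by chance. A footnote should say both.

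### The Day 56 ECG plot anchors its double difference on the Day 1 predose reading, which leaves the Day 56 day effect in and adds reading error; the vital-sign definition also misprints one of its days

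*SAP*

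**What the plan says.** SAP 3.5.4 defines two ECG quantities.

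- **Change from baseline.** "Baseline is defined as the time-matched value from the average of the triplicate recordings on Day -1". Section 6.6.4 tabulates this change; it "will be summarized by treatment and time post-dose and day with descriptive statistics", so Day 56 is covered.
- **Double difference.** Step 1 is to "subtract predose value on Day 1 from all postdose values". Step 2 is to "subtract the value at 0 hours on Day -1 from all other values on Day -1". Step 3 takes the difference of the two at matching times.

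The double difference is tabulated (N, mean, 90% confidence interval) only for readings after the Day 1 treatment, but its mean is plotted for two days: "Mean time-matched double differences in ECG parameters will be plotted against time postdose for Day 1 and Day 56 separately", with one line per treatment. Section 6.6.3 does the same for blood pressure and pulse rate: "Mean time-matched double differences in vital signs will be plotted against time post-dose for Day 1 and Day 56 separately".

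The vital-sign definition in SAP 3.5.3 differs from the ECG one in step 2, which reads "subtract the value at 0 hours on Day -1 from all other values on Day 1".

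**The concern.** A double difference earns its extra terms by subtracting each day's own 0H reading, so that a shift affecting a whole day cancels. That works on Day 1. On Day 56, the anchor named in step 1 belongs to a different day, so the reason for the subtraction is gone while its noise remains.

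Day 56 matters because it is the only day at the 120 mg BID target dose with the full 0 to 12 h ECG and vital-sign schedule (protocol Table 2). Days 43 and 50 have fewer time points. In the unredacted text of the SAP, these plots are the only ECG and vital-sign figures named for Day 56. Protocol 2.2.2.1 reports mean heart-rate increases of 5 to 15 bpm for this drug, so a reader will look here for that signal, with 15 active and 5 placebo participants randomized.

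**Working it through.** The plan states no precision, power or standard deviation for these endpoints, so there is no planned figure to reproduce. The direction follows from the definition; the size needs a model.

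**Notation.** Y(d,t) is the triplicate-mean reading on day d at time t.

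**1. ECG, Day 56, from 3.5.4.**

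DD56(t) = [Y(56,t) − Y(1,0)] − [Y(−1,t) − Y(−1,0)]

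= [Y(56,t) − Y(−1,t)] − [Y(1,0) − Y(−1,0)]

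The first bracket is the tabulated change. The second uses two readings taken before the first dose, is the same at every t, and carries no Day 56 information.

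**2. Model (assumed).** Reading = participant + participant-by-clock-time + day effect (variance τ²) + independent reading error (variance σ²), with day effects independent and exchangeable.

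- Tabulated change, Day 56: the day effects left are Day 56 minus Day −1. Variance 2τ² + 2σ².
- Double difference, Day 56: the day effects left are Day 56 minus Day 1. Variance 2τ² + 4σ².
- Double difference, Day 1: the day effects cancel. Variance 4σ², against 2τ² + 2σ² for the Day 1 change, so it gains precision when τ > σ.

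**3. Ratio of standard errors on Day 56.** With ρ = τ²/(τ² + σ²), the ratio is √(2 − ρ):

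- τ = 0 (ρ = 0): 1.41
- τ = 0.5σ (ρ = 0.2): 1.34
- τ = σ (ρ = 0.5): 1.22
- τ = 2σ (ρ = 0.8): 1.10
- σ = 0 (ρ = 1): 1.00

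Simulation gave the same ratios. At 0H on Day 56 the formula reduces to Y(56,0) − Y(1,0), with variance 2τ² + 2σ², so nothing is lost there.

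**4. Illustration for heart rate (assumed τ = σ = 3 to 5 bpm; 15 and 5 participants).** 1/15 + 1/5 = 0.267.

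- SE of the active-placebo gap, tabulated change: √(4 × 9 × 0.267) = 3.1 to √(4 × 25 × 0.267) = 5.2 bpm.
- SE of the gap, double difference: √(6 × 9 × 0.267) = 3.8 to √(6 × 25 × 0.267) = 6.3 bpm.
- SD of the difference between the plotted and tabulated gaps: this comes from the second bracket alone, with variance 2τ² + 2σ² per participant, giving 3.1 to 5.2 bpm.

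**5. Vital signs as printed in 3.5.3.** Step 2 becomes Y(1,t) − Y(−1,0).

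- Day 56: [Y(56,t) − Y(1,0)] − [Y(1,t) − Y(−1,0)] = Y(56,t) − Y(1,t) − [Y(1,0) − Y(−1,0)]. This subtracts an on-treatment Day 1 reading. The day effects are Day 56 − 2 × Day 1 + Day −1, so the variance is 6τ² + 4σ².
- Day 1: [Y(1,t) − Y(1,0)] − [Y(1,t) − Y(−1,0)] = Y(−1,0) − Y(1,0). The postdose reading drops out.

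If step 2 is read as Day −1, vital signs follow steps 1 to 3 above.

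**The case against.** **The Day 56 derivation may simply be unstated.** The summary sentences tie the definition to readings after the Day 1 treatment, so step 1 could be meant for Day 1 only. That is a fair reading, but then the SAP plots a Day 56 quantity it never defines, and the same edit settles it. If the Day 56 predose reading was the intended anchor, the day effect would cancel, but so would any drug effect present at trough. In simulation, an assumed effect of 5 units with a trough effect of 3 appears as 2. It is not a clean substitute.

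**The better quantity is already reported.** This stands. The Day 56 table uses the time-matched change, no interval or between-arm contrast is planned for the plot, and there are no hypotheses. Redacted text or sponsor standards may add other figures.

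**Version 2 of the SAP added analyses for comparison across studies of the asset.** This is stated generally in the version history, and the double difference was among the additions. It may be a reason to keep such a plot, but it does not justify the Day 1 anchor for Day 56.

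**The bpm sizes are assumptions.** This also stands. Neither document gives τ or σ, and triplicate averaging reduces σ and so the loss.

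**The Day 1 anchor might suit if Day −1 were atypical.** The formula does swap one drug-free day for another. The documents give no reason to prefer Day 1, and the protocol sets Day −1 as the time-controlled baseline.

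**Conclusion.** The point holds as an inexpensive improvement to descriptive secondary safety figures. For ECG, the Day 56 double difference as defined keeps the Day 56 day effect. Under the stated model, its standard error after 0H is between 0 and 41% larger than that of the change already tabulated, and never smaller. For vital signs, the printed step 2 cannot be what was meant, since its Day 1 version contains no postdose reading; this also affects the Day 1 vital-sign double-difference table.

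Three stronger readings are tempting and are not supported.

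- A reader might infer that the plot contradicts the table or is biased. They are two different quantities, separated by one constant per arm with mean zero if there is no systematic Day −1 to Day 1 shift. The time shape is the same. The arms shift independently, so the visible gap between them can differ from the tabulated gap.
- A reader might infer that the plot obscures the 5 to 15 bpm heart-rate effect. The 3.1 to 5.2 bpm offset follows only from assumed standard deviations.
- A reader might apply the ECG formula to vital signs as printed. It applies only once step 2 is corrected.

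The result rests on independent reading errors and exchangeable day effects. The penalty of 2σ² persists if the Day −1 and Day 1 effects are correlated, provided both have the same variance and relate equally to Day 56. No test and no primary PK endpoint is affected.

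**What to change.** 1. In SAP 6.6.3 and 6.6.4, for Day 56 plot the mean change from the time-matched Day −1 baseline, and keep the double difference for Day 1 only.
2. In SAP 3.5.3 step 2, replace the final Day 1 with Day −1, so that it matches 3.5.4.

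The cost is one sentence in each of two sections and one corrected word, with no new derivation: 3.5.3 and 3.5.4 already define the time-matched change, and figure and table would then agree. The downside is that the Day 56 figure no longer shows the same quantity as the Day 1 figure, or as any double-difference plot in other studies of the asset. If that comparison is needed, keep the double-difference plot as a supplementary figure with its Day 56 formula written out.

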7. INTERIM ANALYSES

No formal interim analysis will be conducted for this study.

7.1. Introduction

None.

7.2. Interim Analyses and Summaries

None.

9. APPENDICES

9.1. Categorical Classes for ECG and Vital Signs of Potential Clinical Concern

Categories for QTcF

Degree of Prolongation	Mild (msec)	Moderate (msec)	Severe (msec)
Absolute value	$450 < QTcF \leq 480$	$480 < QTcF \leq 500$	> 500
Increase from baseline		$30 < Increase \leq 60$	> 60

Categories for PR and QRS

PR (ms)	max. ≥ 300	
PR (ms) increase from baseline	Baseline > 200 and max. $\geq 25\%$ increase	Baseline ≤ 200 and max. $\geq 50\%$ increase
QRS (ms)	max. ≥ 140	
QRS (ms) increase from baseline	$\geq 50\%$ increase	

Categories for Vital Signs

Systolic BP (mm Hg)	min. < 90	
Systolic BP (mm Hg) change from baseline	max. decrease ≥ 30	max. increase ≥ 30
Diastolic BP (mm Hg)	min. < 50	
Diastolic BP (mm Hg) change from baseline	max. decrease ≥ 20	max. increase ≥ 20
Supine pulse rate (bpm)	min. < 40	max. > 120

BP: blood pressure.

Measurements that fulfill these criteria are to be listed in report.

CCI

CCI

© 2013 Pearson Education, Inc.

For more information, contact the Office of the Vice President for Research and the Office of the Vice President for Student Affairs.

11. **What is the primary purpose of the following statement?**

9.3. List of Abbreviations

Abbreviation	Term
%CV	coefficient of variation, percent
AE	adverse event
ALT	alanine aminotransferase
AST	aspartate aminotransferase
CCI	
AUC ₂₄	area under the concentration-time curve from time 0 to 24 hours
AUC _τ	area under the concentration-time curve at steady state over the dosing interval τ
BID	twice daily
BLQ	below the limit of quantification
BP	Blood pressure
CaPS	CDISC and Pfizer Standard
CDISC	clinical data interchange standards consortium
CCI	
CFB	change from baseline
CCI	
C _{max}	maximum observed concentration

Abbreviation	Term
$C_{\max,ss}$	maximum observed concentration, steady state
CCI	[REDACTED]
COVID	coronavirus disease
CRF	case report form
CCI	[REDACTED]
dn	dose normalized
ECG	electrocardiogram
CCI	[REDACTED]
HAE	hypoglycemic adverse event
CCI	[REDACTED]
HDL	high-density lipoprotein
CCI	[REDACTED]
LDL	lower-density lipoprotein
LLQ	lower limit of quantification
CCI	[REDACTED]
CCI	[REDACTED]
N/A	not applicable
NC	not calculated
ND	not done
NS	no sample
CCI	[REDACTED]
PK	pharmacokinetic(s)
CCI	[REDACTED]
QRS	time from ECG Q wave to the end of the S wave corresponding to ventricle depolarization
QTc	corrected QT
QTcF	corrected QT (Fridericia method)
SAP	statistical analysis plan
SAS	safety analysis set
SoA	Schedule of Activities
SS	steady-state
CCI	[REDACTED]
T2DM	type 2 diabetes mellitus
TEAE	Treatment emergent adverse event
CCI	[REDACTED]
TSH	thyroid stimulating hormone
CCI	[REDACTED]
CCI	[REDACTED]
